A Pilot Study Testing Benefits of Ursolic Acid (UA) as a Countermeasure To Myopenia and Insulin Resistance in Chronic SCI

3. Objectives

To address the need for an agent that maintains muscle mass and attenuates IR after SCI, we propose a 'first-in-humans with SCI' pilot trial that tests benefits of UA as a countermeasure to sarcopenia and IR.

Aim 1

• To explore effects of UA administration on upper extremity lean mass and peak strength in persons with paraplegia.

Aim 2

• To test effects of UA administration in sedentary individuals with tetraplegia on whole body resting insulin sensitivity, glucose/insulin/inflammatory responses to an oral glucose challenge (OGTT), and whole-body lean mass.

4. Study Endpoints

Primary Outcome Measure(s):

- Change in Muscle Mass Using Dual X-ray Absorptiometry (DXA)

 Time Frame: Baseline, 12 weeks
- 2. Change in Peak Isokinetic Strength
 - a. Time Frame: Baseline, 12 weeks
- Changes in Fasting Insulin Resistance (IR)
 a. Time Frame: Baseline, 12 weeks
- 4. Changes in Glucose Disposal
 a. Time Frame: Baseline, 12 weeks

5. Background

The multi-year COVID-19 pandemic has resulted in a decline of overall physical activity, life-satisfaction, and health within the spinal cord injured (SCI) community.¹ **During the pandemic, people with SCI have experienced health decay to a far greater extent than the general population, primarily due to profound social distancing, fears of social engagement and infection, and restrictions in exercise engagement.² Even without social isolation and exercise restrictions, trauma to the spinal cord is typically associated with physical and metabolic disorders that have wide-ranging effects on almost all body systems.³ Our works,⁴ and the works of other investigators⁵ have reported a level-of-injury dependent myopenia – i.e.,** *clinically relevant muscle wasting* **– which is commonly observed following spinal cord injury (SCI), and ultimately compromises post-SCI function, metabolism, body composition, and health. Adjustments to body composition that accompany SCI-related myopenia include a decline of metabolically active muscle mass accompanying the loss of actively contracting muscle, which reduces whole body caloric expenditure and establishes**

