In a pre-clinical study,⁹ we investigated UA as an agent affecting anabolic, metabolically-linked signaling pathways in muscle, and explored phenotypic outcomes in sublesional muscle following traumatic SCI. Our primary objectives were to examine following experimental SCI i. intracellular mTOR signaling, ii. The expression of related catabolic genes, and iii. The effects on these outcomes with UA treatment. We hypothesize that SCI would i. reduce growth pathways via mTOR signaling, ii. Increase the expression of catabolic genes, and iii. UA will attenuate these SCI-induced changes. In addition, we examined the effect of SCI on physical and functional measures, and whether UA-promoted signaling in muscle translated to improvements in these outcome measures. When examining effects of UA treatment on sublesional muscle mTOR signaling, catabolic genes, and functional deficits following severe SCI in mice we observed that UA treatment significantly attenuated SCI-induced decreases in activated forms of mTOR, and signaling intermediates PI3K, AKT, and S6K, and the upregulation of catabolic genes including FOXO1, MAFbx, MURF-1, and PSMD11. In addition, UA treatment improved SCI-induced deficits in body and sublesional muscle mass, as well as functional outcomes related to muscle function, motor coordination, and strength.

These findings provided first evidence that UA treatment may be a potential therapeutic strategy to improve muscle specific pathological consequences of SCI.

6. Inclusion and Exclusion Criteria

Inclusion Criteria

- 18-65 years of age
- Aim 1: Male and female individuals with paraplegia having chronic (≥ 1 year) complete and incomplete (AIS A/B/C) injuries from T2-T8
- Aim 2: Male and female individuals wi4.th chronic (≥ 1 year) complete and incomplete (AIS A/B/C) injuries from C4-C7

Exclusion Criteria

- Pregnant or planning to become pregnant
- Women who are breastfeeding

Number of Subjects

- Aim 1 will enroll up to 10 participants
- Aim 2 will enroll up to 10 participants

7. Study Recruitment Methods

Recruitment will include IRB-approved flyers posted throughout the Christine E. Lynn Rehabilitation Center for the Miami Project to Cure Paralysis; social media; word-of-mouth at the Christine E. Lynn Rehabilitation Center for the Miami Project to Cure Paralysis; online advertisement using IRB-approved language from flyers, telephone or email contact for those individuals who have previously consented for contact in other studies.

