The co-primary outcomes will be lean mass and peak strength.

- Aim 2 subjects will:
 - Subjects will receive 2 bottles of oral UA every month
 - Subjects will be asked to take 400 mg or 8 capsules (4 in the morning/200mg and 4 at night/ 200mg) daily for 12-weeks.
 - Adherence to the UA intervention will be done once a month by study staff and will entail:
 - collection of used bottle
 - counting remaining capsules, if any
 - calculation of compliance: [(days x 8) capsules remaining]
 - and dispensing a new bottles.

**Education regarding the importance of compliance to the dosing requirements will be part of the monthly drug accountability.

*** Research Studies Subjects will be offered participation in other PM&R and Miami Project to Cure Paralysis studies for which they may be eligible. The possibility of dual enrollment or partial overlap of participation in more than one study is conceivable. This could result in duplication of required assessments subjects would need to complete. However, to simplify participation, reduce the number of visits to our research lab, and mitigate testing redundancy, we may apply test results completed for one study to another in those cases.

- Whole body lean mass will be determined by DXA and CT scan before and after 12 weeks of treatment.
- Before and after the 12-week UA intervention an oral glucose tolerance test (OGTT: 75 g glucose as TrutolTM) will be administrated following an overnight fast.
 - Bloods taken before glucose ingestion will be analyzed for glucose, insulin, and inflammatory biomarkers (TNF-alpha, IL-6, and CRP).
 - Bloods will also be taken at 30-minute intervals for two hours.
- Maximal inspiratory pressure will be measured with the Pro2 Fit device.

Co-primary outcomes will be the fasting IR determined by the HOMA v2 model and the rates of glucose disposal defined by the area under the glucose challenge curve (AUC).

Dual X-ray Absorptiometry (DXA)*

The regional composition for Fat Free Mass (FFM), Fat Mass (FM), % FM, and Lean Mass (LM), in regions of interest including the trunk, arms, android, and gynoid regions will be measured by DXA as described by Gorgey et al., Spinal Cord 2018. Body composition will be measured by whole body scans using a GE

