- Data for the trial will be managed using a secure data repository system database (box or redcap), and through paper and pencil. Regulatory trial management may use the Complion INC e-regulatory system platform. All data collected will be entered into a secured data collection system. All participating centers in this multi-site project will have access to the coded deidentified data collected as a part of the study.

11. Data Management

Randomization

- For Aim 1, the dominant or non-dominant arm assigned to resistance exercise (versus non-exercise) will be randomized in equal numbers using the 'RAND' function in Microsoft Excel.
- No randomization is required for Aim 2.

Data analysis

- Will be performed using a repeated measures design corrected for multiple comparisons (Bonferroni) with co-primary outcomes for Aim 1 of *mass* and *strength*, and Aim 2 for co-primary outcomes of *IR* and *glucose disposal*. Other outcomes will be considered exploratory.
- Non-parametric techniques will be used, or data transformed, if the data fail a test of normality or homogeneity of variance. $\alpha = 0.05$ for all testing will represent the threshold value used to judge whether a test statistic is significant.

12. Confidentiality and Subject's Data Safety

• Physical/paper records will be stored in a locked room at the Miami Project (Christine E. Lynn Rehabilitation Center, [name]) in a lockable file cabinet only accessible to study personnel in the. A security badge is needed to open the office door where data are stored. Access to Miami Project (Lynn Center 2nd Floor) is via a universityissued hallway proximity card after passing a security guard located in the front lobby.

- There are two types of electronic records, 1) source data and 2) pdf versions of all paper and electronic data.
 - Source electronic data will be stored in the original collection location. In addition, a copy of the electronic file may be stored on the Miami Project Server in a working group with restricted access. The Miami Project server is behind UM firewalls and is backed up electronically daily, with tapes of older copies archived off site in a fire/hurricane secure facility.
 - All electronic and paper source data will also be stored electronically as pdf's in an electronic version of the participant's folder. Paper source data will be scanned, and electronic source data will be saved as a pdf.
- Data Storage Duration

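### Aim 2 is worded as a test of UA's effects, but a single uncontrolled before-and-after group cannot separate UA from other change over 12 weeks

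*Combined protocol and SAP*

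**What the plan says.** Section 3 describes the study as a "pilot trial that tests benefits of UA as a countermeasure to sarcopenia and IR". Within it, Aim 1 is to explore, whereas Aim 2 is "To test effects of UA administration in sedentary individuals with tetraplegia" on insulin sensitivity, on the glucose, insulin and inflammatory responses to an OGTT, and on whole-body lean mass.

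The design of Aim 2 is set out in three places:

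- Section 6, on numbers: "Aim 2 will enroll up to 10 participants".
- Section 9, on treatment and timing: "Subjects will be asked to take 400 mg or 8 capsules (4 in the morning/200mg and 4 at night/ 200mg) daily for 12-weeks", and "Before and after the 12-week UA intervention an oral glucose tolerance test" is given. It then states: "Co-primary outcomes will be the fasting IR determined by the HOMA v2 model and the rates of glucose disposal", the latter taken from the area under the glucose curve.
- Section 11, on allocation and analysis: "No randomization is required for Aim 2". The analysis is repeated measures with a Bonferroni correction and a significance threshold of 0.05. Outcomes other than the co-primaries are exploratory.

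No placebo, untreated or historical comparator, run-in or repeat baseline is described for Aim 2. No section limits the interpretation to within-group change or names the missing control as a limitation. The one control in the study, the untrained arm in Aim 1, also receives UA. It controls for exercise and not for UA, and it is not part of Aim 2.

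**The concern.** With everyone on UA and two time points, the only contrast available in Aim 2 is week 12 against baseline. That contrast estimates the effect of UA plus everything else that changed over the 12 weeks. The objective claims a test of the first component alone, and the design does not supply one.

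The protocol's own text makes other change plausible. Section 5 describes pandemic-related loss of activity and fitness and a delayed return to social life. Section 9 allows overlap with other studies and states no restriction on co-interventions. Sampling conditions are standardised on the test day, but nothing standardises or records diet or activity between the two tests.

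The error can run either way. Drift towards better glucose handling could be read as a UA effect. Drift towards worse handling could cancel a real one. Either would mislead the planning of a controlled trial, which is the natural use of a pilot.

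**Working it through.** **Plan's own figure.** There is none to reproduce: the documents give no effect size, SD, power or sample-size calculation for Aim 2.

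**Inputs from the documents.** n = 10 (the maximum, section 6); two co-primaries (section 9); threshold 0.05 with Bonferroni (section 11).

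**Assumptions.** The test is a two-sided paired t-test on change scores (sidedness is not stated). Bonferroni covers the two co-primaries, so each is tested at 0.05 / 2 = 0.025. The true UA effect is zero. The non-UA mean change is d SDs of the change score; d is assumed and shown as a range.

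**Formula.** Under these assumptions the t statistic is noncentral t with 9 degrees of freedom and noncentrality d × √10. The chance of significance is P(|T| > critical value), counting both tails. The critical value is 2.685 at 0.025 and 2.262 at 0.05.

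| Assumed non-UA shift d | Noncentrality d × 3.162 | Significant at 0.025 | Significant at 0.05 |
|---|---|---|---|
| 0 | 0 | 0.025 | 0.050 |
| 0.2 | 0.632 | 0.048 | 0.088 |
| 0.3 | 0.949 | 0.079 | 0.136 |
| 0.5 | 1.581 | 0.192 | 0.293 |
| 0.8 | 2.530 | 0.475 | 0.616 |

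**What Bonferroni does.** For two independent outcomes with no drift, the family error is 1 − (1 − 0.025)² = 0.049. The correction deals with multiplicity; the 0.025 column shows that it does not deal with drift.

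**Masking.** The same table gives the opposite error. Suppose UA truly improved an outcome by 0.8 SD and drift worsened it by 0.3 SD (both assumed). The net shift is 0.8 − 0.3 = 0.5 SD, and the chance of significance at 0.025 falls from 0.475 to 0.192.

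**What a control would do.** In 200,000 simulated trials with shared drift and no UA effect, a 5-versus-5 comparison of change kept the error at about 0.025 for drift of 0, 0.5 and 1.0 SD. The cost is power. For a true 1.0 SD effect at 0.025, power is 0.19 with 5 versus 5 and 0.44 with 10 versus 10, against 0.68 for the single group if drift is exactly zero.

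**Precision of the present design.** The half-width of the 95% CI for mean change is 2.262 / √10 = 0.72 SD of the change.

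**The case against.** The strongest reply is that this is an openly described, small, first-in-SCI pilot, and that the single group is a visible choice and not a hidden error. That is fair as to the design: a single-arm pilot is legitimate for feasibility, safety and variability. It does not cover the wording. Aim 2 says test where Aim 1 says explore, and its co-primaries are tested for significance and are not among the outcomes called exploratory.

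Several stronger readings are tempting, and the documents do not support them.

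- A reader might infer that any significant change will be wrongly credited to UA. Section 11 uses the threshold only to judge a test statistic; it contains no efficacy decision, go/no-go rule or attribution rule. A significant improvement might also be a true UA effect, and a significant worsening would not count as benefit. The supportable word is could.
- A reader might treat the larger shifts as expected. Nothing in the documents supports a particular value. Injuries must be at least a year old, participants are sedentary, blood is drawn after a 10-hour fast with 24 hours free of alcohol and caffeine, and no criterion selects for high baseline insulin resistance. These features limit some sources of drift, though they do not replace a control.
- A reader might add test familiarity as a cause. That fits poorly here, because the co-primaries come from blood analytes. It is more relevant to the strength test in Aim 1.
- A reader might conclude that the significance test must be dropped. It need not be: it is a valid test of within-group change if it is described as one.

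**Conclusion.** The concern holds as a mismatch between claim and design. Aim 2, as designed, can estimate the 12-week change in people taking UA; it cannot say how much of that change is due to UA. This conclusion rests on the absence of any comparator and does not depend on the calculations.

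The size is illustrative. At the Bonferroni level the chance of a significant result with inert UA rises from 2.5% with no drift to 5%, 8%, 19% or 48% per co-primary as the assumed shift goes from 0.2 to 0.8 SD. The corresponding figures at an unadjusted 0.05 are 9%, 14%, 29% and 62%. Small shifts matter modestly and large ones a great deal, and the documents do not show which applies. The figures also assume a two-sided paired t-test and all 10 participants contributing.

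The issue is worth correcting because the correction is cheap. It does not show that the single-arm pilot should not be run.

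**What to change.** 1. In section 3, restate Aim 2 as estimating the 12-week within-person change during UA, and keep all the outcomes it now lists: insulin sensitivity, the glucose, insulin and inflammatory responses to the OGTT, and whole-body lean mass.
2. In section 11, report mean change, SD and 95% CI for the Aim 2 outcomes as planning values for a controlled trial. Keep the planned test of the co-primaries and describe it as a test of within-group change.
3. In section 11, state that Aim 2 results will not be attributed to UA without a controlled comparison.
4. Bring the title and the overall objective in section 3 into line with this. Both speak of testing benefits of UA, and Aim 1 cannot isolate UA either, because its control arm also receives it.

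The cost is revised wording and a few added summary statistics. No participants, visits, samples or control group are added, and no planned test is lost. The downside is a weaker headline claim.

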The loss of muscle mass after SCI has been associated with hastened trajectories pf all-cause cardiovascular diseases (CVD), which have emerged within the past decade as significant sources of morbidity and mortality for persons with spinal cord injuries (SCI).⁶ These trends forecast patterns of illness and death after SCI that increasingly resemble those of the non-disabled general population. Among these CVD risks is the increased hazard for cardiometabolic diseases (CMD), a clustering of interrelated prothrombotic and proinflammatory factors that confers health risks that are equivalent to either coronary artery disease or diabetes.

Notably, these risk equivalents may be experienced without actually having coronary disease or a clinical diagnosis of diabetes, making their occurrence an insidious health threat in need of focused early management.⁷

Ursolic Acid as a Countermeasure to Post-SCI Myopenia and Insulin Resistance Ursolic Acid – naturally occurring triterpene compound – is an herbal-like isolate obtained from the leaves of various plants (rosemary, marjoram, lavender, thyme, and organum), fruits (apple fruit peel), and berries. UA modulates several signaling pathways associated with the development of chronic diseases. Among confirmed benefits of UA administration are anti-inflammatory, anti-oxidant, antiobesity, anti-diabetic, cardioprotective, anti-skeletal muscle atrophy, and thermogenic effects. The mechanisms by which UA exerts these beneficial effects may involve regulation of insulin signaling in adipose tissue, as well as atrophy and metabolic signaling in skeletal muscles through the mTOR signaling pathway.⁸

Recent evidence suggests that the UA has beneficial effects on insulin resistance (IR) and related CMD health risks in persons without SCI, and also slows muscle wasting in instances of musculoskeletal disuse.⁸ Given that 60 percent of the SCI population has a metabolic profile with IR, and that obligatory sarcopenia occurs within the first year following SCI, UA may represent a novel countermeasure to health risks associated with COVID-related social isolation.

Preclinical testing of UA following SCI

Potential benefits of UA for persons with SCI are supported by our pre-clinical work in which UA but not a control compound, maintained muscle mass and muscle function in mice that had undergone experimental spinal cord contusion injuries.

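### Aim 2 neither restricts nor records glucose-lowering treatment or activity, although its glycaemic co-primaries are judged before and after without a control group

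*Combined protocol and SAP*

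**What the plan says.** Section 6 admits to Aim 2 people who are "18-65 years of age" with "chronic (≥ 1 year) complete and incomplete (AIS A/B/C) injuries from C4-C7". Its only exclusions, shared by both aims, are "Pregnant or planning to become pregnant" and "Women who are breastfeeding". The Aim 2 objective in Section 3 describes a narrower group: "To test effects of UA administration in sedentary individuals with tetraplegia".

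Section 9 names the endpoints: "Co-primary outcomes will be the fasting IR determined by the HOMA v2 model", together with the area under the OGTT glucose curve. Both are measured before and after 12 weeks of UA. Fasting glucose and insulin come from the blood sample taken before the glucose drink.

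Four other places might have covered treatment or activity, and none does:
- Blood Analyte Testing (Section 9) sets rules for alcohol, caffeine and fasting only.
- The two monthly Aim 2 visits (Section 8) are for capsule accountability and pregnancy tests.
- Withdrawal of Subjects (Section 13) covers adverse effects, pregnancy, adherence below 80% and the subject's own wish to leave.
- Data analysis (Section 11) names no covariate or sensitivity analysis for medication or activity.

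Section 11 says that Aim 2 needs no randomization. Section 9 allows overlapping enrolment in other studies.

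**The concern.** Both Aim 2 co-primaries are glycaemic, so glucose-lowering treatment acts on them directly. There are two separate problems.

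The first is what HOMA2 measures. It takes measured fasting insulin as an input. If part of that insulin was injected, the result no longer describes the participant's own fasting insulin response. This can happen even when treatment is stable, and it affects HOMA2 only, not glucose AUC.

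The second is change over time. If a drug is started, stopped or altered during the 12 weeks, or activity changes, either co-primary can move. Every Aim 2 participant takes UA, so no comparison group would show the same drift. Because neither treatment nor activity is recorded, the analyst could not find the affected participants afterwards. A pilot's estimated change is likely to inform the next study, so a distorted mean matters even when no test becomes significant.

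Separately, the objective names a sedentary population that the criteria do not require, so the enrolled group need not be the stated one.

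**Working it through.** **Inputs from the documents.** n is at most 10 (Section 6). There is one group and no randomization (Section 11). Alpha is 0.05 with a Bonferroni correction and two co-primaries (Section 11). I read this as 0.05 / 2 = 0.025 each, and I assume two-sided tests because sidedness is not stated. The documents give no SD of change, effect size, power, frequency of glucose-lowering treatment or frequency of treatment change. The plan therefore has no figure to reproduce, and the calculations below are illustrations.

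**Assumptions.** UA has no effect, change scores are normal with SD 1, and a paired t-test is used. Of 10 participants, k have a background shift of s SD in the favourable direction.

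**Step 1: bias in the mean.** Bias = k × s / 10.
- One participant at 2 SD: 1 × 2 / 10 = 0.2 SD.
- Two at 1 to 2 SD: 0.2 to 0.4 SD.
- Three at 1 to 2 SD: 0.3 to 0.6 SD.

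For scale, the true change detectable with 80% power at n = 10 and alpha 0.025 is 1.14 SD. A bias of 0.2 SD is 0.2 / 1.14 = 18% of that, and 0.6 SD is 53%.

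**Step 2: false positives.** The test rejects when |t| > 2.685 (9 df), with t = mean / (SD / √10). A few shifted participants also raise the SD. The expected sample variance is 1 + k(10 − k)s² / 90. For k = 1, s = 2 it is 1 + 36/90 = 1.40, and for k = 3, s = 2 it is 1 + 84/90 = 1.93. In the limit of one very large shift, the mean is s/10 and the standard error is also s/10, so |t| tends to 1, well below 2.685.

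Simulated rejection rates (repeat runs differ by about 0.1 percentage point):

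| k of 10 | s (SD) | bias (SD) | all rejections | false improvement only |
|---|---|---|---|---|
| 0 | – | 0 | 2.5% | 1.25% |
| 1 | 1 | 0.1 | 2.5% | 2.0% |
| 1 | 2 | 0.2 | 2.2% | 2.1% |
| 2 | 1 | 0.2 | 3.4% | 3.2% |
| 2 | 2 | 0.4 | 4.0% | 4.0% |
| 3 | 1 | 0.3 | 5.2% | 5.2% |
| 3 | 2 | 0.6 | 8.2% | 8.2% |

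One changed participant does not raise the overall rate, although more of the errors then fall in the favourable direction.

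**Step 3: noise without bias.** Suppose treatment does not shift the mean but doubles the change SD in 3 of 10 participants (an assumption). Power at a true mean change of 1 SD then falls from 68% to 43%.

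**Step 4: population wording.** Section 3 restricts Aim 2 to sedentary people. Section 6 has no activity criterion, and no definition or measure of activity appears elsewhere. This mismatch needs no assumption.

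**The case against.** The strongest reply is that this is a first pilot of up to 10 people, for which broad eligibility is a defensible choice. Each participant is their own control, so stable treatment largely cancels from the mean change. Recording treatment and analysing with and without those who changed would deal with change-related bias without excluding anyone. The protocol only links to the HOMA2 calculator and says nothing about injected insulin. The word sedentary may simply contrast Aim 2 with the exercise programme of Aim 1.

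Much of this stands. Exclusion is not the only remedy, the sedentary mismatch is a separate wording matter, and the HOMA2 point applies only to insulin users whose fasting sample contains injected insulin. But the recording on which the reply relies is not in the plan. The medical-history form in the recruitment registry (Section 7) is not a trial record and cannot show a change during the study. Recording alone also leaves open how HOMA2 is analysed in an insulin user.

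Three stronger readings are tempting and not supported:
- A reader might infer a large inflation of false positives. Mean shifts of 0.3 and 0.5 SD do give 7.9% and 19.2% at alpha 0.025, but only if all ten participants shift equally. If 5 of 10 shift by 1 to 2 SD, false improvement reaches 12.9% to 30.5%. The documents give no reason to expect a change that widespread.
- A reader might take the chance that someone in the group is treated as the chance of bias. Bias needs treatment to change within 12 weeks, and the documents give neither frequency.
- The Background says that "60 percent of the SCI population has a metabolic profile with IR". This describes the population that UA is meant to help. It says nothing about drug use, and the same section notes that cardiometabolic risk can exist without diagnosed diabetes.

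**Conclusion.** The point holds as a gap in eligibility and recording. The stated criteria admit people whose measured insulin, or whose treatment change during the study, would distort a co-primary, and the plan has neither a control group nor a record that would reveal it. The main harm is to the estimate: 0.2 SD from one participant shifted by 2 SD, and up to 0.6 SD if three shift by that much. The harm to the test is modest when few people change. These sizes rest on assumed shifts, normal change scores and a two-sided paired t-test at 0.025. The gap itself rests on the text alone. It shows that such people can enter, not that they will. The amendment is cheap and should be made, but the point does not show that Aim 2 would produce a false result.

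**What to change.** - **Insulin and HOMA2.** In Section 6, Aim 2, add an eligibility criterion so that HOMA2 is not computed from samples containing injected insulin. Alternatively, state in Section 11 that such participants are left out of the HOMA2 analysis. The sponsor's clinicians should set the wording.
- **Recording.** Record glucose-lowering treatment and activity at the four existing Aim 2 visits (screening, two monthly, final), without restricting any clinically needed change.
- **Analysis.** In Section 11, prespecify a sensitivity analysis of both co-primaries without participants whose treatment or activity changed. Report it beside the main analysis, not in its place, because it selects on events after baseline.
- **Population.** Reconcile sedentary in the Section 3 objective with Section 6, either by adding a defined criterion or by removing the word.

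The cost is a short amendment and a brief set of questions at visits already planned. If eligibility is narrowed, the recruitment pool shrinks slightly. The registry holds more than 3000 people, but across all injury levels, so the Aim 2 pool is smaller than that. The sensitivity analysis has a smaller n: if two participants change, it rests on 8.

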UA will be sourced as Biotech Nutritions Ursolic Acid Gelatin Free Non-GMO capsules (i.e. form) ; 200mg (4 total capsules, 50mg each) taken twice daily by mouth with food and a non-alcohol-containing drink. UA is a non-Rx nutraceutical obtained without prescription. We will neither claim an FDA 'brand' for the product, nor propose a new or extended indication for its use.

Manufacturer: Biotech Nutritions [name] Ph: [name]

- Aim 1: will couple UA administration at doses that increase muscle mass with strengthening exercise performed in one arm only.
 - Subjects will receive 2 bottles of oral UA every month. Subjects will be asked to take 400 mg or 8 capsules (4 in the morning/200mg and 4 at night/ 200mg) daily for 12-weeks
 - Adherence to the UA intervention will be done once a month by study staff and will entail:
 - collection of used bottle(s)
 - counting remaining capsules, if any
 - calculation of compliance: [(days x 8) capsules remaining
 - and dispensing a new bottle(s).

**Education regarding the importance of compliance to the dosing requirements will be part of the monthly drug accountability.

*** Research Studies Subjects will be offered participation in other PM&R and Miami Project to Cure Paralysis studies for which they may be eligible. The possibility of dual enrollment or partial overlap of participation in more than one study is conceivable. This could result in duplication of required assessments subjects would need to complete. However, to simplify participation, reduce the number of visits to our research lab, and mitigate testing redundancy, we may apply test results completed for one study to another in those cases.

- During this period, one upper limb (only), randomized by selection, will undergo exercise conditioning three times weekly using a strengthening program we have established to increase muscle mass and strength in people with SCI. The other arm will remain untrained as a control receiving the same whole body dose of UA.
- Lean mass will be examined before and after 12 weeks of treatment using dual-ray absorptiometry (DXA) and non-contrast CT scan of both arms, with the area of interest identified from the glenohumeral joint distally to the ulnar styloid.
- Peak isokinetic strength of both arms at 90 degrees of flexion will be tested in elbow flexion and extension on a Biodex dynamometer.
- Maximal inspiratory pressure will be measured with the Pro2 Fit device.

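### Ursolic acid is sold without prescription, yet current users are eligible and outside use is not recorded, so the 12-week change attributed to it may not start from an untreated baseline

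*Combined protocol and SAP*

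**What the plan says.** Section 3 sets the purpose: "we propose a 'first-in-humans with SCI' pilot trial that tests benefits of UA as a countermeasure to sarcopenia and IR". Section 4 measures muscle mass, peak strength, fasting insulin resistance and glucose disposal as changes, each with "Time Frame: Baseline, 12 weeks". Section 9 describes the product: "UA is a non-Rx nutraceutical obtained without prescription".

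The inclusion criteria in Section 6 are age ("18-65 years of age") and injury duration, grade and level. The exclusions are two: "Pregnant or planning to become pregnant" and "Women who are breastfeeding". The numbers are small: "Aim 1 will enroll up to 10 participants" and "Aim 2 will enroll up to 10 participants".

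Section 9 measures adherence by counting returned study capsules once a month. Its pre-test restrictions for blood sampling cover alcohol, caffeine and food, not supplements. Section 8 dispenses the first bottles to Aim 2 participants at the consent and screening visit, so there is no run-in. In Aim 1 the untrained control arm is exposed to UA as well (Section 9). Aim 2 is a single group without randomization (Section 11).

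**The concern.** Reading a 12-week change as an effect of UA requires a baseline free of UA. As printed, someone already buying UA meets every criterion, and that person's baseline is an on-treatment value. If they have little further response to gain, they pull the mean change toward zero.

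The opposite can also happen. A participant who starts an anabolic agent or a muscle-building supplement during the 12 weeks may gain lean mass or strength for reasons unrelated to UA. Nothing printed would bring either case to light: there is no supplement history at screening, no instruction or question about non-study UA, and the capsule count cannot see it.

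Neither aim has a UA-free group in which such use could balance out, and with at most 10 people per aim each participant carries at least a tenth of the mean.

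**Working it through.** The plan gives no effect size, standard deviation or power calculation, so there is no figure of its own to reproduce. The eligibility gap is settled by reading. Its possible size can only be illustrated under assumptions.

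**Inputs from the plan.** n = 10 per aim at most (Section 6); alpha = 0.05 with Bonferroni correction and two co-primaries per aim (Section 11), so 0.05/2 = 0.025 each if the correction is over those two.

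**Assumptions.** A two-sided one-sample t-test on the 12-week change (Section 11 does not state sidedness); changes normal with SD 1; 200,000 simulated trials per cell.

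**Dilution by prior users.** Suppose k of 10 already take UA and show no further change, while the others change by δ SD on average. Then

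mean change = δ × (1 − k/10).

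One prior user dilutes it by 1/10 = 10%, two by 2/10 = 20%. With δ = 1.0:

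| Prior users of 10 | Mean change (SD) | Power, alpha 0.05 | Power, alpha 0.025 |
|---|---|---|---|
| 0 | 1.0 | 80% | 68% |
| 1 | 0.9 | 68% | 54% |
| 2 | 0.8 | 55% | 40% |
| 3 | 0.7 | 42% | 29% |

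The result depends on the assumed effect. With two prior users, power at alpha 0.05 falls from 62% to 40% for δ = 0.8 and from 92% to 69% for δ = 1.2. At alpha 0.025 the falls are from 47% to 27% and from 84% to 54%. Across the range the loss is about 20 to 30 percentage points.

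**Inflation by agents started on study.** Suppose UA has no effect and k of 10 start an agent that adds g SD to the outcome. Then

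shift in mean change = k × g / 10,

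which is 0.1 SD per starter for g = 1 and 0.2 SD for g = 2. The false-positive rates are:

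| Starters of 10 | Nominal 5%: g = 1 / g = 2 | Nominal 2.5%: g = 1 / g = 2 |
|---|---|---|
| 1 | 5.1% / 4.6% | 2.4% / 2.2% |
| 2 | 6.6% / 8.4% | 3.4% / 4.0% |
| 3 | 9.8% / 16.1% | 5.2% / 8.1% |

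One starter biases the mean but leaves the test near its nominal level, because that participant's gain also widens the spread.

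**Which comparison is exposed.** In Aim 1 the randomized contrast is trained against untrained arm in the same person. A systemic agent reaches both arms and largely cancels unless it interacts with training. That contrast estimates the effect of exercise under UA. The effect of UA itself, which Section 3 names as the objective, rests on the pre/post change, and that is exposed. In Aim 2 the pre/post change is all there is.

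**The case against.** The strongest reply is that this is a pilot with at most 10 people per aim, that Aim 1 is described as exploratory, and that broad eligibility is a defensible choice. The documents give no prevalence of UA, anabolic or supplement use, so nothing shows that even one user would enrol. The dilution figure also assumes that prior users take a similar dose and have nothing further to gain. Extra self-bought UA on study would be a departure from the planned dose rather than an effect of something else. All of this stands, and it limits how much weight the numbers can bear. It does not close the gap: a current user is eligible as written, and the plan would not know.

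Readers might infer more than the documents support in four ways:

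- **That Aim 1's randomized comparison is compromised.** It is within person, so systemic agents largely cancel.
- **That one person starting an anabolic agent would produce a false positive.** The calculation shows otherwise.
- **That the bias can be stated in kilograms of whole-body lean mass for Aim 1.** Aim 1 measures lean mass of the arms. Whole-body lean mass belongs to Aim 2, where Section 11 names insulin resistance and glucose disposal as the co-primaries.
- **That screening for supplements would make the change attributable to UA.** Without a UA-free comparison it would not; screening removes one avoidable source of error.

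**Conclusion.** The point holds for the uncontrolled baseline-to-12-week change in both aims. The printed criteria admit people already taking the study product, and nothing visible records non-study UA or muscle-building agents during follow-up. The finding covers the public text, from which some pages were removed.

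The direction depends on the pattern of use: prior UA use dilutes the change, agents started on study can inflate it, and stable long-term use mainly adds noise. The size is unknown because prevalence is not given. Conditional on two prior users of 10 with no further response and a true effect of 1.0 SD in the others, the mean change falls by 20% and power from about 80% to 55% at alpha 0.05. Conditional on gains of 1 to 2 SD, each on-study starter adds 0.1 to 0.2 SD to the mean. These are illustrations, not estimates of what will happen. The case for acting is that prevention is cheap and that use not recorded at the time could later be reconstructed only from recall.

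**What to change.** - **Section 6:** exclude current or recent use of UA supplements, within a period before baseline that the investigators set.
- **Section 9:** ask about non-study UA, and about starting, stopping or changing anabolic agents or muscle-building supplements, at screening, at each monthly accountability contact and at the final visit. Record the answers with dates. Nobody is asked to stop prescribed treatment.
- **Section 11:** prespecify a sensitivity analysis of the co-primaries that excludes participants with such use, reported beside the main analysis. With so few people, also list the affected participants.

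The cost is one eligibility line, one question at visits already scheduled, and one extra analysis. The downside is that a few volunteers become ineligible. The same record can serve the separate point on glucose-lowering drugs, which the printed criteria also leave open, so one medication and supplement form would cover both.
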